5.1. Health-Related Purpose

* Are any instruments used for health-related purposes including diagnosis or treatment?

Yes No

5.2. Specific Medical Mobile Application

* Does this study involve a medical mobile application focused on specific health related conditions and not just general wellness activities?

Yes No

5.3. Instrument Assessment

Please contact the FDA Regulated Research Oversight Program if you are unsure whether your project involves assessing the safety and/or efficacy of an instrument.

* Do any aims of the study involve assessing the safety and/or effectiveness of those instruments?

Yes No

5.4. Data Submitted to FDA

* Will data from the proposed activity be submitted in an application to the FDA?

Yes No

Reporting Results

Studies with potential for discovery of incidental or adventitious findings require special consent form language. Review the guidelines on consent form language in [**HRP-503 Consent Form Template**](#).

1. Originating Procedure

* Identify the procedure that could create the findings. (e.g., imaging scan, laboratory blood test, depression screening questionnaire, etc.)

Laboratory tests may identify conditions previously unknown to subjects, such as kidney disease, liver disease, or diabetes.

2. Results Released

* Will findings be released to subjects?

Yes No

2.1. Type of Results

* Describe which findings will be released to subjects, and why. Explain what the subject (or their doctor, if applicable) could do with this information.

All abnormal laboratory findings will be released to the patient as they could be clinically important and may require alteration of current treatment plans. The supervising physicians for this study will use laboratory results to guide treatment related to the aims of the study (hypertension and cardiovascular risk reduction) as well as to provide appropriate management and/or referral to other physician(s) for management of abnormalities not related to the specific aims.

2.2. Entity Assessing Release

The IRB would not expect (and in some cases will not allow) the dissemination of information to subjects generated from tests or procedures that are considered experimental.

* Indicate who will assess whether the information should be reported to subjects and the qualifications of those making such assessments. If it is based on a score, address whether the samples are run in a CLIA-certified laboratory.

The supervising physicians ([name], [name], and [name]) for this study will guide reporting of incidental findings. [name] is a general practitioner and [name] is a family physician and both are skilled in the evaluation of common laboratory tests (such as those used in this study) and management of abnormalities in these tests.

2.3. Reporting Timeframe

* Provide the timeframe for reporting findings to subjects, and if applicable, their physicians.

Within 1 month.

2.4. Reporting Process

* Describe the process for reporting results to subjects, including who will disclose results and whether any additional resources are in place. If results will be placed in the subjects' medical records, please indicate this.

One of the supervising physicians will review patient data, including laboratory tests, on a monthly basis. Incidental findings/abnormal results will be discussed with the community health workers, who will then relay this information to subjects and any recommendations/instructions for treatment or other follow-up. Subjects will be able to access treatment or further work-up for abnormalities as needed at Hospital Obras Sociales Monseñor Gregorio Schaffer in San Lucas Tolimán, Guatemala (where [name] is the attending physician). Abnormal results will be noted in the patient's medical record.

Subject Identification: Medical Records

1. Medical Record Use

* Will medical records be used to identify subjects or records?

Yes No

1.1. CRDS Usage

CRDS assists UW investigators with developing data queries and delivering data from the UW Health Enterprise Data Warehouse (EDW) to be used in feasibility assessments, recruitment of participants, pilot studies, and retrospective analyses.

* Will you use the Clinical Research Data Service (CRDS) to identify subjects via these records?

Yes No

1.2. Record Identification Details

* Describe how eligible subjects will be identified using medical records, including 1) which records will be accessed and 2) who will identify eligible subjects.

Patients with hypertension who may be eligible to participate in the study will be identified by community health workers (CHWs) and other study personnel (including PI [name] and research assistant [name]) from lists of such patients maintained by the community health worker program, as well as from records stored in the secure CommCare database of patients identified as having hypertension through the concurrent study of hypertension diagnosis by CHWs, which is also funded by this grant.

Risks and Benefits

1. Direct Benefits Intended

For this type of research there are generally no direct benefits to subjects. The response to this question, "There are no direct benefits to subjects", would be acceptable.

* Are any of the research activities intended to directly benefit subjects?

Yes No

1.1. Direct Benefit Details

* Describe how subjects will benefit from the research activity.

Controlling hypertension reduces the risk of stroke, coronary artery disease, congestive heart failure, end-stage renal disease, peripheral vascular disease, as well as overall mortality. Providing statins, +/- aspirin, for hypertensive patients who are at high risk of heart attack and stroke or have a history of these complications greatly reduces the risk of these potentially fatal or life-altering events.

2. Potential Benefits to Society

Describe how the research might help future patients.

* Describe the importance of the knowledge reasonably to be gained from this study and what benefit the research may provide to society.

If we can show that CHWs can effectively manage hypertension with remote physician supervision, this would have important implications for global hypertension control. Currently, less than 10% of patients with hypertension in low- and middle-income countries (LMIC) have blood pressure at goal. If this is shown to be an effective strategy, task sharing with CHWs and other frontline health workers could help to improve treatment of hypertension in LMIC, which often lack sufficient numbers of more highly trained health workers, such as physicians and nurse practitioners, to address this important global health problem.

3. Direct Physical Intervention

A physical intervention refers to study procedures that may pose a risk (however minimal) to a subject's body (e.g., blood draws, MRI scans, drug or device trials, exercise, dietary restrictions/supplements). Examples of activities that are NOT physical intervention include obtaining informed consent and administering surveys.

* Does this study involve direct physical intervention with subjects?

Yes No

3.1. Physical Risks and Discomforts

* Describe the most common or frequent physical risks and discomforts expected related to study participation (e.g. pain, bruising, redness/itching).

Bruising is a common outcome from drawing blood (venipuncture). Blood pressure measurement does cause mild arm discomfort.

3.2. Unusual Physical Interventions

* Does the protocol involve physical interventions that will NOT be conducted in clinical settings (e.g., blood draws in a medical clinic) or designated research areas (e.g., exercise testing in an approved lab) where they would normally occur?

Yes No

3.2.1. Outside Physical Interventions

* Describe the physical interventions performed outside a clinical setting or designated research area.

Measurement of blood pressure and other vital signs; blood draws.

3.2.2. Interventions Location

* Describe where the interventions will occur.

These interventions will primarily occur in clinical settings (clinical sites in rural communities run by the network of community health workers with which we are collaborating), but may occur during home visits.

3.2.3. Emergency Plan

- * Describe the plan for handling emergencies, including who will provide medical oversight, if applicable.

Emergencies resulting from these interventions are not anticipated. Guatemalan co-investigator [name], study team physician [name], and PI [name] will be available to consult with community health workers (CHWs) remotely as needed and transport to the hospital in San Lucas Tolimán can be arranged so that [name] or [name] can evaluate a patient in person as needed. All CHWs are trained in basic emergency care.

4. Potential Psychosocial Risks

For this type of research the risks to subjects are generally limited to the risk of breach of confidentiality. The response to this question, "There is a risk of breach of confidentiality", would be acceptable.

- * Describe any potential psychosocial risks to subjects, such as psychological stress or confidentiality risks (including risk to reputation, economic risks, and legal risks).

Since personal and medical information will be collected from subjects, there is a risk of potential breach of privacy/confidentiality.

If conducting activities in participants' homes, there's a risk associated in situations of suspected abuse which involve mandatory reporting requirements and informing subjects of this reporting requirement.

5. Procedures to Minimize Risks

The response to this question should address how the risk of breach of confidentiality will be minimized. For example, it could be described that the study team has several measures in place to protect against a breach of confidentiality, such as limiting the number of people who view identifiable information, coding study instruments, storing study data in restricted areas and on computers that are password-protected, only transmitting coded data outside the institution (if data will be shared), and using a secure web-interface to transmit data off-site (if data will be shared).

* Describe the procedures in place to minimize risks from all interventions performed for research purposes. This should include activities in place to identify, monitor, mitigate, and eliminate risks to the degree possible.

Study interventions will be performed in a private room or, at a minimum, out of earshot of other people in order to ensure privacy and confidentiality. Data will be collected on encrypted, password protected smartphones or tablets using the CommCare application, which is also password protected and encrypted. Study data will be stored on CommCare's secure server, which is HIPAA compliant, secure University of Wisconsin servers, and secure computers in Guatemala. Any hard copies of data containing PHI will be stored in locking filing cabinets in controlled-access facilities.

Subject Population

1. Total Subjects

You must provide an integer. If you are enrolling a range of subjects (e.g., 50 to 100 subjects), enter the larger number.

* Provide the number of subjects that will be enrolled at sites for which UW Madison is serving as the reviewing IRB.

30

2. Inclusion Criteria

* Describe the main inclusion criteria.

Adults age 18 or greater with diagnosis of hypertension AND blood pressure (BP) $\geq 140/90$ OR currently taking antihypertensive medication.

3. Exclusion Criteria

* Describe the main exclusion criteria.

- Pregnancy
- Severe comorbid condition(s) with life expectancy less than 1 year

4. Targeted Populations

Populations could be racial/ethnic, sex, or gender (this also applies to gender identity, or lack thereof).

* Will this study target or exclude specific populations?

Yes No

Special Populations Justification

1. Justification

If more than one special population is enrolled, separate justifications should be provided for each unique population.

* What is the justification for the inclusion of these subjects?

Study recruitment and activities will occur in the municipality of San Lucas Tolimán, Guatemala. A large majority of the population in this area belongs to the Kaqchikel Maya ethnic group and speaks both Spanish and the Kaqchikel language. Average income in these communities is less than \$1000/year.

2. Safeguards

Include the measures that will be taken to minimize any potential coercion or undue influence in recruitment and ongoing participation in the study.

* Describe the additional safeguards that have been included in this study to protect the rights and welfare of these subjects.

Potential subjects will be assured that their participation will have no bearing on services that they currently receive or may receive in the future from our local partner, the San Lucas Mission. All consent materials will be translated into Spanish and informed consent will be obtained by CHWs who are bilingual in Spanish and Kaqchikel (which is not generally used as a written language).

Recruitment Methods

1. Recruitment Plan

This description should address what methods will be used, when and how often they will be used, and how many times potential subjects will be contacted.

- * Describe the recruitment plan for this study.

Subjects will be recruited by community health workers (CHWs) from patients identified as having hypertension during the hypertension screening and diagnosis study as well as from among patients previously known to have hypertension by the CHWs.

2. Recruitment Material Upload

Upload recruitment materials such as recruitment emails, letters, phone scripts, brochures, or advertisements.

There are no items to display

3. Approved Recruitment Database Usage

- * Are you using an IRB approved recruitment database to disseminate recruitment materials or to contact subjects?

Yes No

Subject Screening

1. Preliminary Eligibility Screen

- * Will subjects undergo a preliminary screen to determine basic eligibility?

Yes No

1.1. Screening Materials

* Upload a copy of the screening questionnaire.

Screening Questionnaire - Feasibility study.docx

1.2. Data Retention

If you are retaining screen data, the previously uploaded questionnaire/script should address this and include authorization language for maintaining PHI if HIPAA applies.

* Will you be retaining screen data from subjects who do not enroll in the study?

Yes No

2. Planned Study Procedures Before Obtaining Consent

Examples include fasting, discontinuing medications, etc.

* Will there be any procedures performed before informed consent is obtained from subjects (apart from screening)?

Yes No

2.1. Procedure(s) Details

* Describe the applicable study procedures that will be conducted before informed consent is obtained from subjects.

Potential subjects will be instructed to come to study screening/enrollment fasting in case they do qualify as baseline labs will be drawn, including fasting lipid panel and fasting glucose. For patients who have been diagnosed with hypertension, but are not currently taking medication, a blood pressure will be checked to see if they qualify (BP $\geq 140/90$). For women who are capable of conceiving (premenopausal, no history of tubal ligation or hysterectomy) and who are not sure if they are currently pregnant, a urine pregnancy test will be required prior to enrollment.

Remuneration and Costs

1. Payment

* Will subjects be compensated to participate in the study?

Yes No

2. Costs

* Will subjects incur any costs as a result of study participation (pharmacy preparation fees, payment for a device, billing of study procedures to subjects insurance)?

Yes No

Privacy and Confidentiality

1. Privacy Plan

Privacy is defined in terms of having control over the extent, timing, and circumstances of sharing oneself (physically, behaviorally, or intellectually) with others. In the context of research, this primarily pertains to methods used to obtain information about subjects or the setting in which research takes place.

* Explain how the subjects' privacy will be protected. (e.g., research intervention is conducted in a private room).

Study interventions will be performed in a private room or, at a minimum, out of earshot of other people in order to ensure privacy and confidentiality.

2. Level of Identifiability

* Select how subjects are identified in the data. Check all that apply.

Directly: Direct Identifiers stored on data (e.g., name, initials, phone number, SSN, or medical record number, stored on data)

Coded or Indirect Identifiers: data includes a link to direct identifiers (e.g., name, initials, phone number, SSN, or medical record number linked to data but stored separately)

No Identifiers (De-identified, Anonymous, or Anonymized): stored data is stripped of all identifiers

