CHWs will meet with patients at enrollment visit and monthly thereafter. All study data will be collected using the CommCare application running on Android smartphones or tablets.

At enrollment, information on basic demographic information, past medical history, and current medications will be collected. CHWs will measure blood pressure, height and weight. Patients will also be administered the Hypertension Self-Care Activity Level Effects (H-Scale) questionnaire and the Patient Assessment of Chronic Illness Care (PACIC) survey on their satisfaction with their current hypertension treatment. They will be assessed for side effects of current medications and signs and symptoms of possible complications of hypertension, including ischemic heart disease, cerebrovascular disease, heart failure, and kidney disease. Blood will be drawn by venipuncture or capillary sample to assess lipid profile, serum creatinine, sodium, chloride, potassium, ALT and blood glucose.

Based on information entered by the CHWs into the CommCare application designed for this study, the application will provide recommendations (and underlying rationale for these recommendations) for prescription of antihypertensives (amlodipine and/or losartan OR enalapril) and medications to reduce cardiovascular risk (aspirin and atorvastatin) if indicated, lifestyle modification, and referral to the supervising physician ([name]) if indicated for potential complications of hypertension.

CHWs will then provide these interventions assisted by recommendations from the application. These procedures (aside from the enrollment panel of lab tests and questionnaires described above) will repeat at monthly visits.

CHWs will be able to contact [name], [name], or PI/PD [name] during the visit as needed for advice on patient management. After each visit, clinical data will be uploaded to CommCare's secure server and reviewed within one week of the visit by [name], [name], and/or [name], who will verify the current treatment plan and contact the coordinators of the CHW program if any changes to treatment are necessary, including the addition of other medications outside of the treatment algorithms per their clinical judgement. In the case that changes are necessary, CHWs will contact patients via phone or visit them at home to communicate and carry out changes.

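### Pregnancy is an exclusion, but the entry urine test is required only of women who are unsure, so a woman who is sure she is not pregnant but mistaken is enrolled untested

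*Protocol*

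**What the plan says.** Protocol, Subject Population, item 3 (Exclusion Criteria) lists two main exclusions, and pregnancy is one of them. Item 2 of the same section opens eligibility to "Adults age 18 or greater with diagnosis of hypertension", with no upper age limit and no restriction by sex, so women who could be pregnant are within the target population.

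Protocol, Subject Screening, item 2.1 (Procedure(s) Details) gives the testing rule. It first defines women able to conceive as those who have not reached menopause and have had neither a tubal ligation nor a hysterectomy. It then adds a second condition. For those women "who are not sure if they are currently pregnant, a urine pregnancy test will be required prior to enrollment".

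Protocol, Research Design and Procedures, item 3 (Study Procedures and Interventions) describes what happens at enrolment. The application may recommend "prescription of antihypertensives (amlodipine and/or losartan OR enalapril) and medications to reduce cardiovascular risk (aspirin and atorvastatin) if indicated". The next step is: "CHWs will then provide these interventions assisted by recommendations from the application". A physician can be contacted during the visit when advice is needed, but routine physician review follows the visit.

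**The concern.** The exclusion is unconditional, but the test that enforces it is conditional on the woman's own doubt. Her certainty is what removes the test. Asking her therefore cannot reveal a pregnancy she does not know about, whereas a test could.

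Two things are at stake. The first is eligibility: someone the study means to exclude could be enrolled without anyone knowing. The second is safety, in a limited sense. Drugs can be provided by a community health worker at the enrolment visit itself, so the eligibility check is the last planned barrier before the first prescription. For this group, the visible text makes that barrier self-report alone.

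**Working it through.** The plan gives no figure to reproduce, and the SAP (4.3) states that no power analysis was done. The check is a reading of the exclusion against the testing rule, followed by a bound on numbers.

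**Step 1. Apply the rule to each kind of woman.**

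| Able to conceive? | What she says | Test required? | Result under the protocol |
|---|---|---|---|
| No | any | No | Pregnancy not in question |
| Yes | Sure she is pregnant | No | Excluded by the pregnancy criterion |
| Yes | Unsure | Yes | Excluded if positive, otherwise may enrol |
| Yes | Sure she is not pregnant | No | May enrol on self-report |

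The exclusion can fail only in the last row, and only when the woman is mistaken.

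**Step 2. Look for another check before the first prescription.** Pregnancy appears in the visible text in three places: the form's generic prompt on special populations, the exclusion criterion, and the testing rule. The description of study procedures names no pregnancy test. That silence is weak evidence, because the description is a brief overview and does not repeat even the urine test that the screening section requires. It shows only that the visible text offers no second check.

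**Step 3. Bound the numbers.** The one usable input is the planned enrolment of 30 (Subject Population, item 1). Let T be the number of enrolled women who are able to conceive and sure they are not pregnant, and let M be the number of those who are mistaken. Then

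0 ≤ M ≤ T ≤ 30.

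T is also the number of extra tests among enrolled subjects if the second condition is dropped. The value 30 would be reached only if every subject were a woman able to conceive and certain of her status. The documents give neither the sex and age mix nor any rate of unrecognised pregnancy, so neither T nor M can be estimated, and M may be zero. A woman who tests positive and is therefore not enrolled adds one further test outside this count.

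**The case against.** The strongest reply is that the deciding documents are not visible. The screening questionnaire is listed as an upload (Subject Screening, item 1.1) and is the natural place to ask about pregnancy and to settle who counts as unsure. The CommCare forms and algorithms that shape prescribing are not shown either. If either asks about the last period or contraception, or treats any doubt as uncertainty, the gap narrows. This stands, and it limits the point to the rule as written. It does not remove the point, because the protocol's own statement of who must be tested leaves certain women out.

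A second reply is that item 2.1 answers a prompt about procedures before consent, so a later test could exist elsewhere. That is possible. However, the sentence governs testing before enrolment, and no later test appears in the visible text.

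A third reply is that asking first and testing those in doubt is a legitimate approach, and that being unsure is a broad category. Both are fair, and they make the affected group smaller. They do not help the woman who has no doubt and is wrong.

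Three stronger readings are tempting, and the documents do not support them:

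- A reader might take the time to routine physician review (data are uploaded to a "secure server and reviewed within one week of the visit") as the length of unsafe exposure. Nothing suggests that the review would reveal a pregnancy that was neither reported nor tested, so the interval does not measure the problem.
- A reader might take the absence of a pregnancy test from the enrolment blood panel as proof that no other check exists. The study's test is a urine test and would not be listed there.
- A reader might cite the protocol's remark that laboratory tests can uncover conditions unknown to subjects. That remark concerns incidental findings such as kidney or liver disease and says nothing about how reliable self-reported pregnancy status is.

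**Conclusion.** The point holds in a limited form. The testing rule does not fully enforce the study's own pregnancy exclusion: a woman able to conceive who is sure she is not pregnant, but mistaken, is enrolled untested and may be given recommended drugs at that visit. The number affected lies between 0 and 30 by the size of the study alone, cannot be narrowed from the documents, and may well be zero.

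The conclusion assumes that the unseen questionnaire and application forms do not already require a test of these women.

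A reader might infer that the documents show fetal harm from the named drugs. They do not: they give no reason for the exclusion and state no drug risk in pregnancy. The point rests on an exclusion that is incompletely checked before prescribing. A reader might also infer that pregnancy arising during follow-up goes unmonitored. The monthly forms are not shown, so this is a question for the sponsor and not part of the finding. Nothing here alters the agreement outcome or the other analyses in SAP 4.3. The change is worth making because it is cheap and bears on safety, not because a large problem has been shown.

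**What to change.** Drop the self-report condition. Suggested wording for the enrolment procedures: *Before the first study prescription, every woman who meets the screening section's definition of being able to conceive will have a urine pregnancy test. A positive result excludes her under the existing pregnancy criterion.* The existing test for unsure women before consent can stay, and a negative result there need not be repeated the same day. The screening questionnaire and CommCare forms should be aligned with the new rule.

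The cost is at most about 30 extra urine tests among enrolled subjects, of a kind the plan already uses; the true number is probably smaller but cannot be derived. No extra visit should be needed. The protocol treats screening, enrolment and the baseline blood draw as one occasion ("Potential subjects will be instructed to come to study screening/enrollment fasting in case they do qualify as baseline labs will be drawn"), and consent is taken at the study site. The one drawback is that a woman tested after consent may be excluded after consenting. The supervising physicians should specify what care or referral follows a positive result.
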